**D. PII De-Identification of Data Used for this Study:**

1. When will you destroy the PII and/or the code linking the PII with the study ID?

As soon as data collection is complete

2. What is the method you will use to de-identify the data?

Each PII is linked to a unique study ID. Only the study ID will be used on any written material, with the exception of a signed consent form. The link between PII and study ID will be stored on a password protected, encrypt computer maintained by the PI. This file linking the PII and study ID will be destroyed after data collection is completed.

3. Is your research data governed by HIPAA (U.S. clinical data remaining within the covered entity)?

Yes  No X

a. If yes, who is doing the de-identification?

b. If yes, what level of de-identification will you achieve (Limited data set? De-identified?)

**E. Data Storage and Analysis:**

One of the keys to protecting PII is the proper use of tools to share and conduct your analysis. JH and JHSPH offers several options for you to consider. Please select the system that you plan to use to protect your study data by clicking the box. Consult JHSPH IT for assistance if needed.

**JH Virtual Desktop:** The Hopkins Institute for Clinical and Translational Research (ICTR) provides a virtual Windows desktop (SAFE Desktop). It includes productivity software

such as Microsoft Word and Excel, as well as statistical software, including SAS, Stata, R, R Studio, and Python. 100 GB of storage space is provided.

- JHSPH SharePoint and File Shares:** These systems provide a managed and secure platform for your research project. They also provide a built-in encrypted backup solution.
- JHSPH RedCAP:** These are departmentally managed applications. RedCAP is an application designed for collaborative research projects.
- JHSPH HPCC:** High Performance Computing Cluster (HPCC: <https://hpc.e.jhu.edu/>) can provide the high capacity computing required for very large data sets.
- JHBox:** Johns Hopkins Box (JHBox) is a secure cloud-based file sharing service which enables people to collaborate and share information and may be accessed through any device: desktop, laptop, phone, or tablet with appropriate permissions. JHSPH IT recommends that investigators not use JHBox as a primary storage location, but use it instead for initial data collection, sharing results, and other collaborative information with the research team.
- Independent Departmental Servers and Systems:** These servers are typically managed by departmental or research team IT staff. Because these servers are not centrally managed by JHSPH IT, all documentation regarding data security protections will need to be provided by the owner/administrator of the server. This responsibility may fall to the data owners (PI).
- Other:** Please provide details regarding any other systems being utilized. Examples may include servers and applications located at another university participating in your study or a 3rd party web-based application.

#### **F. Other Data Security Measures:**

In addition to the details regarding data collection, please review the following questions. This additional information will be utilized to assist in the development of a comprehensive Data Security plan. This would include the systems used to analyze the data, data security contacts and additional requirements.

1. During the analysis phase, do you plan to use computer systems that are not managed by JHSPH or JH? Yes  No  If yes, please explain:
2. Do you have a designated person on your research team other than the PI who is the technical contact for a Data Security plan? Yes  No  If yes, please provide a contact name:
3. Does your sponsor have other specific data security requirements for the study data? Yes  No  If possible, please explain:
4. Please add any other information that you believe is relevant to data security.

#### **G. Certificate of Confidentiality:**

All NIH studies include Certificate of Confidentiality protections with the grant; the consent form must include the C of C language provided in our template. Other funders may obtain C of C protections through NIH. (<https://humansubjects.nih.gov/coc/index>)

Does the study have Certificate of Confidentiality protections?

Yes X No

**H. JHM Clinical Records:**

Will you use clinical data of 500 records or more from Johns Hopkins Hospital and its affiliates?

Yes  No X

If yes, please complete the JHM Data Security Checklist available on the JHSPH IRB website: [www.jhsph.edu/irb](http://www.jhsph.edu/irb) and upload a copy of the checklist to the “Miscellaneous” section.

**VII. Risks of the Study:**

A. Describe the risks, discomforts, and inconveniences associated with the study and its procedures, including physical, psychological, emotional, social, legal, or economic risks, and the risk of a breach of confidentiality. These risks should be described in the consent documents.

There are minimal risks associated with this study. One risk is if the participants are critical of the program or local context and tribal activities. During FGDs, we will refrain from using identifying information and ensure that no written documents have identifying information included. We will also stress at the beginning of the FGD the importance of maintaining confidentiality about what is said during the discussion. Another risk may be an inconvenience with attending five, 3-4 hour meetings over the course of two years. During meetings snacks, coffee and water will be provided to all participants to help make them more comfortable. Participants will also receive an incentive to participate.

B. Describe the anticipated frequency and severity of the harms associated with the risks identified above; for example, if you are performing “x” test/assessment, or dispensing “y” drug, how often do you expect an “anticipated” adverse reaction to occur in a study participant, and how severe do you expect that reaction to be?

We do not anticipate any harms associated with this study.

C. Describe steps to be taken to minimize risks. Include a description of your efforts to arrange for care or referral for participants who may need it.

Risks are considered minimal, but cannot be fully eliminated. We will take the following steps to minimize risks:

1. *Institutional Review Boards at JHSPH and locally.* The study research plan, study instruments and consent forms will be reviewed by an IRB at Johns Hopkins School of Public Health and by the local IRBs.
2. *Informed consent.* We will provide potential respondents a clear opportunity to understand the study objectives and procedures, to assess study risks and benefits, and, verbally, to give or decline consent or assent freely and without pressure or penalty.
3. *Focus Group discussions in a safe, private location.* The study will rely on the local expertise and judgment of local field staff and supervisors to identify where interviews might best be carried out.
4. *Data Storage and Protection.* No unique identifiers will be collected in data collection forms or handwritten notes and the location of interviews will not be recorded.

5. *Privacy concerns:* At the beginning of each FGD, the importance of not using names and identifying information will be reviewed so as to maintain confidentiality of participants.

D. Describe the research burden for participants, including time, inconvenience, out of pocket costs, etc.

Participants will be asked to participate in five, 3-4 hour focus group discussions.

E. Describe how participant privacy will be protected during data collection if sensitive questions are included in interviews.

No sensitive questions will be included in the interview. However, we will still refrain from using PII in the interviews so as to maintain privacy.

### **VIII. Direct Personal and Social Benefits:**

- A. Describe any potential direct benefits the study offers to participants (“payment” for participation is not a direct personal benefit).

There will be no direct benefits to the study participants.

- B. Describe potential societal benefits likely to derive from the research, including value of knowledge learned.

This research will provide knowledge about what contributes to implementation and sustainability of mental and behavioral health programs in tribal settings. We know very little about how to sustain evidence-based programs, and this research is intended to generate preliminary evidence about what might help contribute to sustaining these types of programs in low resource contexts.

### **IX. Payment:**

- A. Describe the form, amount, and schedule of payment to participants. Reimbursement for travel or other expenses is not “payment,” and if the study will reimburse, explain.

The study will reimburse for travel and associated costs to attend the FGDs. In addition, participants will receive an incentive of \$50 per FGD.

- B. Include the possible total remuneration and any consequences for not completing all phases of the research.

If participants completed all 5 FGDs, they will receive up to \$250 in gift cards. If they do not participate in all FGDs, they will not receive this total amount, but there will be no other consequences for not completing the project. Additional other amounts will include travel and accommodation costs of approximately \$150 per participant per FGD meeting. Depending on the location of the meeting and who is traveling, this is not anticipated to be paid for all participants. These FGDs are taking place during pre-planned Hub activities (parent grant) and some participants will already be traveling and have costs covered by the Hub grant.

### **X. Study Management:**

#### **A. Oversight Plan:**

1. Describe how the study will be managed.

The study will be managed by [name] for the duration of study collection. [name] will work with Drs. [name], [name], [name] and [name] to provide management and oversight of all field and data collection activities. The PI and co-investigators will ensure adherence to the IRB approved research plan.

2. What are the qualifications of study personnel managing the project?

[name] is an Assistant Scientist in the Department of Mental Health. She has worked with the Center for American Indian health and field staff for the last 1.5 years. She will be assisted by Drs. [name] and [name] who are the PIs of the parent grant this K01 is leveraging (Hub grant). [name] is a research associated at JHU and has a master's in social work and has led field based activities for the Center for American Indian Health for the last 20 years.

3. How will personnel involved with the data collection and analysis be trained in human subjects research protections? (Use the JHSPH Ethics Field Training Guide available on the JHSPH IRB website: [www.jhsph.edu/irb](http://www.jhsph.edu/irb).)

[name] will be the primary person involved with data collection. Other faculty on the application have existing CITI certificates that will remain current throughout the course of this project. Any field staff who assist with data collection will be trained using the JHSPH Ethics Field Training Guide.

4. If the PI will not personally be on-site throughout the data collection process, provide details about PI site visits, the supervision over consent and data collection, and the communication plan between the PI and study team.

The PI will be personally on site throughout data collection processes.

**B. Recordkeeping:**

Describe how you plan to ensure that the study team follows the protocol and properly records and stores study data collection forms, IRB regulatory correspondence, and other study documentation. For assistance, contact [[contact]](mailto:[contact]).

Consent forms, and handwritten notes will be stored in a locked filing cabinet at JHU that will only be accessible by the PI. No data or forms will be accessed or allowed to be taken out of the room directly by anyone other than them. The PI will take responsibility for ensuring that files are destroyed once the study is complete.

**C. Safety Monitoring:**

1. Describe how participant safety will be monitored as the study progresses, by whom, and how often. Will there be a medical monitor on site? If yes, who will serve in that role?

Participant safety is not considered to be at risk due to participation in this qualitative study. There will not be a medical monitor on site for this research.

2. If a Data Safety Monitoring Board (DSMB), or equivalent will be established, describe the following:

a. The DSMB membership, affiliation and expertise.

N/A

b. The charge or charter to the DSMB.

N/A

c. Plans for providing DSMB reports to the IRB.

N/A

5. Describe plans for interim analysis and stopping rules, if any.

Transcripts and related materials from each FGD will be analyzed iteratively to inform the following FGD.

**D. Reporting Unanticipated Problems/Adverse Events (AEs) to the IRB (all studies must complete this section):**

Describe your plan for reporting to the IRB and (if applicable) to the sponsor. Include your plan for government-mandated reporting of abuse or illegal activity.

The Principal Investigator will report serious adverse events to the JHSPH IRB. If there is any abuse reported during a focus group, the PI will report this to appropriate Tribal Authorities. With experience from previous studies with the program communities, the study team is knowledgeable of how to report this type of event without revealing study participation.

**NOTE:** The IRB does not require PROMPT reporting of all AEs, only those that are **unanticipated, pose risk of harm to participants or others, and are related to the study.** Anticipated AEs may be reported with the Progress Report.

**F. Collaborations with non-JHSPH Institutions:**

For studies that involve collaboration with non-JHSPH institutions, complete the chart below by describing the collaboration and the roles and responsibilities of each partner, including the JHSPH investigator. This information helps us determine what IRB oversight is required for each party. Complete the chart for all multi-collaborator studies.

**Insert Name of Institutions in Partner column(s); add additional columns if necessary.**

	JHSPH	Partner 1	Partner 2

Primary Grant Recipient	X		
Collaborator			

**For the following, indicate “P” for “Primary”, “S” for “Secondary” (as appropriate to role and level of responsibility.) Add additional items if useful.**

1.	Human subjects research ethics training for data collectors	P		
2.	Day to day management and supervision of data collection	P		
3.	Reporting unanticipated problems to the JHSPH IRB/Sponsor	P		
4.	Hiring/supervising people obtaining informed consent and/or collecting data	P		
5.	Execution of plan for data security/protection of participant data confidentiality, as described in the Data Security and Confidentiality Protections section above	P		
6.	Biospecimen processing, storage, management, access, and/or making decisions about future use	N/A		

## Sust-AIns: Sustainment of Suicide Prevention Programs in American Indian Settings

### Study Protocol and Statistical Analysis Plan

**Data sources.** To calibrate the model and check our modeling assumptions, we used data from an annual stakeholder survey of program implementers. The survey administered the Program Sustainability Assessment Tool (PSAT; Luke et al., 2014), which uses the PHPCS framework to measure program capacity for sustainability. The PSAT was administered annually from 2018-2022; additional items from the Sustainment Measurement System Scale (Palinkas, 2020) and questions assessing the impact of COVID-19 were added in 2021. While much implementation science research naturally focuses on implementation outcomes, we also considered sustainment strategies' impact on clinical outcomes. To do so, we used data from participants of a larger study and data from a surveillance system, which recorded suicide-related clinical events.

**Modeling program sustainability.** We modeled key barriers' dynamic impact on program sustainability outcomes. We represented some barriers as model "stocks," or elements that function as "containers" (e.g., of people, money, personal trust, etc.) whose levels can accumulate or deplete over time, and represented others as factors impacting stock levels (i.e., "inflow" or "outflow" rates from the stocks). We populated the model with data from the stakeholder surveys, using Python 3.7 to conduct constrained optimization for model calibration (Van Rossum & Drake, 2009).

**Modeling clinical outcomes.** We used microsimulations to model client-level suicidal behaviors and to estimate the effects of program sustainability interventions on these health outcomes. We developed a multi-state model (Williams et al., 2017) to describe how people transition between various potential "states" of suicidal behaviors.

**Simulations.** We conducted computational simulations of various intervention scenarios using the models described above. We designated December 2018 as the start of the simulated time frame (Month 0) and calculated outputs for the following 60 months. We conducted four simulation scenarios to evaluate key strategies' impact on program sustainment outcomes and clinical outcomes (operationalized as the incidence of non-lethal suicidal behavior—ideation, self-harm, and attempts). Factors that contribute to sustainment were defined as our outcomes and were represented as stocks whose levels we tracked under each simulated scenario. These included: *resources available, program services available, community trust in program, community and external collaborators, number of staff, and number of clients*.

We fitted *Model 1 (Baseline)* to reflect observed trends in the stakeholder survey data from December 2018 through October 2022, without simulating any sustainment strategies.

For *Model (2)*, we examined the impact of an *Increased Funding* strategy (corresponding to the PHPCS "funding availability" domain). We simulated an increase in funding sources by creating

a dummy constant stock called *increased funding*, which flowed into *resources available* at a rate of 0.01 (initiating at Month 0).

For *Model (3)*, we examined the impact of a multifaceted approach to *Enhanced Program Management* (corresponding to the PHPCS “organizational capacity” domain). We conceptualized this strategy as decreasing *conflicting priorities*, measured by survey questions on whether funding comes from diversified sources, whether organizational leaders efficiently manage program resources and staff, and whether the organization has capacity to supervise program providers. We simulated this intervention by decreasing the value of *conflicting priorities* by 10% in Month 0.

Finally, for *Model (4)*, we examined the impact of a hypothetical *Leadership Development* intervention (corresponding to the PHPCS “environmental support” domain). To simulate this strategy, we directly increased the value of *strong program leadership* by 10% in Month 0.

We performed sensitivity analyses to test the robustness of our assumptions and estimate uncertainty for our simulated results. We used Approximate Bayesian Computation to generate sets of system dynamic model parameters (Sunnåker et al., 2013) and then sampled multiple sets of parameter values using Latin hypercube sampling (Loh, 1996).

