### C. Study Implementation:

1. Describe the procedures that are complex, insert a table below to help the reviewer navigate.

The proposed research focuses on phase 1 (“*participate*”) of a CBSD approach. We will conduct a **series of five FGDs** that will occur during planned U19 Hub site meetings or at

other times that are convenient for participants. Focus Group Discussions (FGDs) will last approximately three to four hours each. During **FGD 1**, participants will be oriented to systems thinking and systems modeling. They will be asked to describe CL’s implementation using model building scripts (scripts 1-3). Following the FGD, I will add and refine the model diagram based on Implementation Science models and theoretical frameworks. This diagram will serve as the basis for the “implementation subsystem” and allow modeling of how different aspects of program implementation interact. During **FGD 2**, we will use model building scripts (scripts 1-3) to facilitate discussion of the factors involved in program sustainability. Participants will map out these factors to create a “sustainment subsystem.” During **FGD 3**, I will present the models back to participants and to discuss how implementation and sustainment subsystems interact to create our full systems dynamic model (script 4).

Figure 3 provides a simplified example of this process. On the left, implementation of the CL program depends on tribal government support which helps to reduce suicide rates. Reduction of suicide rates in turn help to increase tribal government support. We then expand this model of implementation (on the right) to include other relevant program, practice setting, and ecological factors that influence sustainment of the CL program. For example, tribal government support increases local acceptance of the program, which increases program reach meaning that more people are registered and receive CM, thereby decreasing suicide rates and reinforcing tribal government support.

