During **FGD 4**, we will generate a list of hypothesized strategies (scripts 5 & 6) for how CL sustainability can be enhanced based on our overall model of the combined two subsystems. For example, if program reach (e.g. delivering case management to all those registered in surveillance system) is thought to be a problem, strategies might involve increasing service capacity (i.e. increasing proportion of time allocated to case-management, changing batching case management visits by geographic location). FGD participants will first generate an exhaustive list of strategies for targeted sustainment variables based on hypotheses, as well as, strategies known in the literature. Finally, we will break into setting specific groups to identify any setting specific considerations. Participants will then be asked to prioritize their lists based on applicability and feasibility within their settings. The final product will be a list of 5 general and 3 setting specific strategies, ranked by priority and feasibility. The models and specific strategies will serve as the basis for future systems science modelling based on existing data (IRB application to be submitted at a later date).

Finally, during **FGD 5**, we will review CL's mission and purpose and use the simulation results as a decision tool to help stakeholders select among competing strategies. We will then write sustainability action plans with specific steps for implementing each strategy or combination of strategies. By the end of FGD 5, stakeholders will have selected a strategy (or set of strategies) and have an actionable sustainability plan for how to implement these strategies in their own contexts.

*Fit of CBSD approaches:* All FGDs will be recorded. There will be one note taker from the local communities who will take notes regarding unspoken interactions and dynamics during the group sessions. At the completion of each FGD, we will gather anonymous feedback about the sessions using an evaluation survey. FGD recordings, notes and evaluation surveys will be reviewed and analyzed prior to the next scheduled FGD. The PI and the research associate will listen to the recordings and mark and transcribe sections that relate to how systems thinking approaches fit with participants existing thinking and/or the cultural context.

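### Does taking incidence from a client-level simulation deny credit to strategies that widen reach, and so mis-rank them?

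*Combined protocol and SAP*

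**What the plan says.** In the Study Protocol and Statistical Analysis Plan, the paragraph on modeling clinical outcomes states: "We used microsimulations to model client-level suicidal behaviors". A multi-state model is then used to "describe how people transition between various potential 'states' of suicidal behaviors". The data come from participants of a larger study and from a surveillance system.

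The Simulations paragraph gives the clinical outcome as "operationalized as the incidence of non-lethal suicidal behavior—ideation, self-harm, and attempts". It names six sustainment factors as the outcomes, ending with "number of staff, and number of clients", and these are "represented as stocks whose levels we tracked under each simulated scenario". Outputs run for 60 months from December 2018 under Baseline, Increased Funding, Enhanced Program Management and Leadership Development.

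The Research Plan, section V.C (Study Implementation), gives a simplified example in which government support raises local acceptance, "which increases program reach meaning that more people are registered and receive CM, thereby decreasing suicide rates". Under FGD 4 it describes reach as "delivering case management to all those registered in surveillance system", a possible problem that strategies might address. Under FGD 5 the intention is to "use the simulation results as a decision tool to help stakeholders select among competing strategies", after a review of the program's mission and purpose.

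The text does not state the denominator, the time unit, whether the simulated population is fixed or grows with the client stock, or whether people not reached are included.

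**The concern.** A comparison between scenarios is easiest to read when every scenario has the same population at risk. Here the simulated behaviors are those of clients, and the number of clients may change with the strategy. If incidence is taken among clients, there are three ways to compute it, and none credits reach:

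- A count of events rises as clients are added.
- A rate per client ignores what newly reached people would have experienced without the program.
- A fixed cohort of starting clients leaves out people reached later.

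Yet the Research Plan's example treats reach as a route by which the program lowers suicide rates, and the simulation results are meant to inform the choice among strategies. A strategy that averts more events in the community could then appear worse than one that averts fewer.

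**Working it through.** The documents give no event rate, coverage or scenario result, so there is no figure to reproduce. Every input below is an assumption.

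**Setup.** Let c be the share of a fixed population who are clients, RR the client-to-non-client event rate ratio, x the relative rise in clients and y the relative fall in the client rate.

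- Change in count among clients: (1+x)(1−y) − 1
- Change in rate among clients: −y
- Change in the fixed population: [1 − c(1+x)(1 − RR(1−y))] / [1 − c(1−RR)] − 1

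**Two contrasting strategies.** A has x = 20%, y = 0. B has x = 0, y = 2%. Among clients, A is +20% (count) or 0% (rate), and B is −2% either way, so B ranks first.

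In the fixed population with RR = 0.8 and c = 0.5:

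- A: (1 − 0.5×1.2×0.2)/(1 − 0.5×0.2) − 1 = 0.88/0.90 − 1 = −2.2%
- B: (1 − 0.5×(1 − 0.8×0.98))/0.90 − 1 = 0.892/0.90 − 1 = −0.9%

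A now ranks first. At c = 0.3 the figures are −1.3% and −0.5%; at c = 0.7 they are −3.3% and −1.3%.

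**When the order reverses.** A averts more than B when x(1−RR) > RR·y, that is when RR < x/(x+y) = 0.20/0.22 = 0.909. The threshold does not depend on c, but the example requires c(1+x) ≤ 1, so c can be at most 1/1.2 = 83%. With x = 10% the threshold is 0.10/0.12 = 0.83; with x = 5% it is 0.05/0.07 = 0.71.

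**When it does not.** People taken into case management may be at higher risk than those who are not, so an observed RR could exceed 1. With RR = 1.2 and c = 0.5:

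- A: (1 + 0.5×1.2×0.2)/(1 + 0.5×0.2) − 1 = 1.12/1.10 − 1 = +1.8%
- B: (1 + 0.5×(1.2×0.98 − 1))/1.10 − 1 = 1.088/1.10 − 1 = −1.1%

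B ranks first, as it does among clients, and the fixed population itself shows wider reach as harm.

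**A second setup.** Take 1,000 people at risk and a non-client rate of 0.20 per year. Strategy C has 200 clients at 0.10 and strategy D has 400 at 0.12. Community events are 200×0.10 + 800×0.20 = 180 for C and 400×0.12 + 600×0.20 = 168 for D, so D is better although its per-client rate is higher. Reversal needs a client ratio above (0.20−0.10)/(0.20−0.12) = 1.25, and here the ratio is 2. With a non-client rate of 0.13 the required ratio is 0.03/0.01 = 3, and doubling the clients is not enough.

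**The scenarios actually planned.** Strategies A and B were chosen to isolate reach and per-client effect. Models 2 to 4 act on resources, conflicting priorities and program leadership. None is defined as changing only reach or only the client rate, so the documents cannot show whether a reversal arises among them.

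**The case for a change.** The case for a change is that client-level is the only population term attached to the microsimulation, that no simulated non-clients are described, and that reach is part of the program theory. The client stock shows that reach has risen but not what it averts. The planned sensitivity analyses vary system dynamic parameters and, as described, leave the outcome's denominator alone. On that view, a fixed population holding clients and people not yet clients should supply the main clinical result.

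The first part stands as an observation: the denominator and the population at risk are not described. The remedy does not follow from it.

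- Client-level can simply mean individual-level, as opposed to the program-level stocks. The multi-state model is described for people, and surveillance data are among its sources, so a wider population is not excluded.
- A fixed-population result needs non-client transition rates. The documents do not show that these can be estimated. Without them the result rests on an assumed range of confounded ratios, and the working shows that the ratio alone decides the direction.
- Taking surveillance registrants fixed at Month 0 as the population would omit people newly registered through wider reach, which repeats the fault it is meant to cure.
- The sustainment stocks are the named outcomes and clinical events are considered in addition. Nothing in the documents selects a strategy on incidence alone.

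**Conclusion.** No change to the plan is needed. The mechanism is real: if incidence is confined to clients, reach is not credited in the clinical result, and under assumed inputs the order of two strategies can reverse (−2.2% against −0.9% in a fixed population at 50% coverage and a ratio of 0.8, against 0% and −2% as client rates). This rests on a per-client reading that the text does not establish, on strategies unlike the four scenarios, and on a rate ratio below 0.91. Above that value the order is the same either way.

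What is left is missing description. The SAP is written in the past tense about simulations already run, so the analysts know which population was simulated and can say so with the results: the denominator, the time unit, and whether people not reached were included. If only clients were simulated, the clinical figures are read together with the client stock that the plan already tracks. Replacing the main clinical output with a fixed-population figure would exchange an unstated denominator for an unsupported rate ratio, with no clear gain. The outcome is already confined to non-lethal behavior, so it makes no claim about mortality.
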